7.3 Observations during days 7-28 post-vaccination

Parents will be asked to record only significant health events affecting subjects (see 7.2 a-f) defined as events that required medical attention or interfered with daily activities. Adverse events that begin on day 7 or later and are still present on day 28 will be clinically followed to the final resolution date.

7.4 Reporting of Serious Adverse Events

Parents will be asked to advise the investigator as soon as possible of any Serious Adverse Event (SAE, defined below) that occurs while subjects are enrolled in the study. Details of the SAE are to be explored in sufficient detail to enable the investigator to complete the provincial AEFI form and to assess the likelihood that it was caused by the vaccination. SAEs will be identified on the adverse event section of the e-CRF. Since the vaccine will have been approved for distribution, it will not be a requirement to report SAEs that are clearly unrelated to the study vaccination, such as respiratory virus infections.

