1. INTRODUCTION

A variety of childhood autoimmune diseases such as granulomatosis with polyangiitis, juvenile idiopathic arthritis, inflammatory bowel disease or systemic lupus erythematosus are now controlled using immunosuppressive medications. These commonly include biologics such as tumor necrosis factor-, interleukin 1 or 6 - antagonists along with disease-modifying anti-rheumatic drugs (DMARDs) such as methotrexate. Disease control comes at the risk of increased infection. Many important childhood infections can be prevented with effective vaccines, most of which are administered early in life. For vaccines that can be safely given while on immunosuppressive medication, a blunted and/or rapidly waning immune response may occur. This has been demonstrated for several routine vaccines, but there is virtually no such data available for prevention of travel-related diseases in immunocompromised children.

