5.1.3 Monitoring

Investigators will be made aware of any concerns with respect to vaccine reactions or changes to the stability of the underlying disease condition of the subject(s).

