9.2.1 Safety observations

The 2 vaccines in this study are both licensed for use in the age group of the study population. Reactions will be documented in order to identify potential differences in the rates of local reactions and/or significant health events between groups.

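### Section 7.4 waives reporting of clearly unrelated SAEs without saying whether they must still enter the study record, and the SAE definition it promises is missing

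*Combined protocol and SAP*

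**What the plan says.** Section 7.4 makes four statements in turn.

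- Notification: "Parents will be asked to advise the investigator as soon as possible of any Serious Adverse Event", for as long as the subject is enrolled.
- Assessment: the investigator gathers enough detail to complete the provincial form and "to assess the likelihood that it was caused by the vaccination".
- Recording: "SAEs will be identified on the adverse event section of the e-CRF".
- Waiver: because the vaccine will already be approved, "it will not be a requirement to report SAEs that are clearly unrelated to the study vaccination, such as respiratory virus infections".

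The section introduces the term as "Serious Adverse Event (SAE, defined below", but no definition follows in 7.4, 7.5 or any later section. The contents list titles 7.4 with the word severe, while the body heading says serious.

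Elsewhere, the Introduction says of the immunosuppressive drugs that "Disease control comes at the risk of increased infection". Section 5.1.3 says investigators will be told of concerns about vaccine reactions or "changes to the stability of the underlying disease condition of the subject(s". Section 9.2.1 says reactions are documented to "identify potential differences in the rates of local reactions and/or significant health events between groups".

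**The concern.** The waiver does not name who would otherwise receive the report. The protocol uses the verb for two things: parents telling the investigator (the visit descriptions in 5.2.3) and staff informing the province and the federal agency (5.2.3 and 7.5). A site could therefore leave a hospital admission for infection off the eCRF without breaching the text.

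That would make recording depend on an individual judgement of cause. In a randomised trial, background events are better handled by counting them in both arms and letting the comparison speak. The example chosen, respiratory infection, is also a kind of event to be expected in immunosuppressed adolescents. With no seriousness criteria, sites have no stated standard for either half of the decision: whether an event is serious, and whether it is clearly unrelated. What is at stake is a complete account by arm of serious events in a small pilot.

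**Working it through.** The plan contains no SAE rate, SAE count or safety sample size to reproduce. Its one design calculation (18 per group, 36 in all, raised to 60 in section 9.3) concerns seroconversion and does not bear on this point.

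**Step 1. What the waiver can mean.**

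- Outward reporting only: supported by the stated reason (the vaccine is approved), by the mention of the provincial form, and by the recording sentence, which has no causality condition.
- Study record as well: not excluded, because the waiver closes a section that covers notification, recording and outward reporting together, and names no recipient.

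**Step 2. What is collected, by period.**

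| Period | Rule | Depends on cause? |
|---|---|---|
| Days 0–6 after each dose | 7.2 diary; 7.2(f) covers doctor and ER visits and hospitalization | No |
| Days 7–28 after each dose | 7.3, events needing medical attention or interfering with activities | No |
| Day 29 after dose 1 to Visit 3 | 7.4 only | Yes, on the wider reading |

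Section 7.5 ends safety observations at day 28. The schedule in 5.2.1 marks a safety review at Visits 2 and 4 only. It also marks a health assessment and eligibility review at Visit 3, but 5.2.5 describes a health history at Visit 1 only, and the Visit 3 text lists no safety review.

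**Step 3. Length of the exposed interval.** Section 6.2 separates the doses by 6 to 7 months.

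- 6 months: about 183 − 28 = 155 days.
- 7 months: about 213 − 28 = 185 days.

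This uses the schedule table and 6.2. The Visit 2 text in 5.2.3 also lists giving dose 2, which conflicts with the table and must be reconciled.

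**Step 4. What parents are told.** Visit 1 asks for prompt SAE reports over the next 6 days; Visits 2 and 3 ask for 28 days; 7.4 covers all of enrolment. Visit 2 falls on day 28–35, so its instruction runs to day 28 + 28 = 56 at the earliest and 35 + 28 = 63 at the latest. On the visit instructions alone, the time before Visit 3 with no request to parents is 183 − 63 = 120 to 213 − 56 = 157 days.

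**Step 5. Illustration of size.** Assumptions, none from the documents except the total of 60: equal arms of 30; SAE risk p in the exposed interval; share f of SAEs left unrecorded. Expected recorded SAEs per arm = 30 × p × (1 − f). Chance of at least one = 1 − [1 − p(1 − f)]^30.

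| p | Expected, f = 0 | Expected, f = 50% | Expected, f = 75% | P(≥1), f = 0 | P(≥1), f = 50% |
|---|---|---|---|---|---|
| 2% | 0.60 | 0.30 | 0.15 | 0.455 | 0.260 |
| 5% | 1.50 | 0.75 | 0.38 | 0.785 | 0.532 |
| 10% | 3.00 | 1.50 | 0.75 | 0.958 | 0.785 |

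An extreme case: 4 of 30 (13.3%) have serious infections and all are left out. The record shows 0/30, with an exact two-sided 95% upper limit of 1 − 0.025^(1/30) = 11.6%, below the proportion that occurred.

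A formal comparison would be weak regardless. Fisher power at 30 per arm for 5% v 20% is 0.24 with full capture and 0.04 with half unrecorded. Even 4/30 v 0/30 fully captured gives a two-sided p of 2 × C(30,4)/C(60,4) = 2 × 27,405/487,635 = 0.11.

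**The case against.** The best answer is that 7.4, read as a whole, concerns outward reporting. Parents notify every SAE, the eCRF sentence is unconditional, and the reason given for the waiver is regulatory. The investigator already assesses causality, so much of the fix spells out what the authors probably meant. This is the more natural reading, and it stands as such. It does not settle the matter, because the text never says so and the wider reading breaches nothing.

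A reader might go further and infer that a planned between-arm SAE comparison is distorted by causality opinion. The documents do not support that. Section 9.2.1 names local reactions and significant health events, and 7.3 defines the latter without reference to cause. Nor do they support treating infection as a risk of the vaccine or the higher antigen content: the Introduction ties it to medication, which both arms take. No mechanism for unequal loss between arms is shown. The summary calls the trial double-blinded while 6.3 describes withholding the formulation only from parents and guardians, so the blinding of the causality assessor is unclear, but that does not demonstrate differential loss.

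A reader might also infer that disease-flare admissions would be waived, or that events in the long interval leave no trace. Both go too far. Nothing says a flare would be classed as clearly unrelated, 5.1.3 separately routes changes in disease stability to investigators, and Visit 3 includes an eligibility and contraindication review. None of these is a systematic SAE record, however.

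**Conclusion.** The point holds as an ambiguity in SAE ascertainment with a missing definition. It is worth correcting because correction is cheap. It is not a demonstrated bias in any planned analysis.

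Its reach is mainly the 155 to 185 days between day 28 after dose 1 and Visit 3, when 7.4 is the only explicit adverse-event collection rule. This assumes that dose 2 is given at Visit 3, 6 to 7 months after dose 1. The number of events at risk cannot be estimated from the documents; the figures in the illustration rest on assumed rates. They show only that a filter reduces an already small count in proportion, and that each SAE in a trial of 60 matters descriptively rather than for testing.

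**What to change.** - In 7.4, state that every SAE from dose 1 to Visit 4 is entered on the eCRF whatever its presumed cause, with the investigator's causality assessment in a separate field.
- State that the waiver for clearly unrelated SAEs applies only to outward reporting to the province and PHAC.
- Insert the promised seriousness criteria, kept apart from the diary severity grades in 7.2, and align the contents-list title with the section heading.
- Reconcile the SAE instructions to parents at Visit 1 (6 days) and at Visits 2 and 3 (28 days) with the enrolment-long duty in 7.4. Without this, an eCRF rule cannot recover events that parents were not asked to report.
- In 9.2.1, list all SAEs descriptively by arm, with related SAEs as a subset.

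The cost is about a paragraph of text, one eCRF field, one consistent instruction to parents and a few extra SAE entries. Sample size and visits are unaffected.

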7.5 Collecting safety observations from subjects

At Visits 2 and 4 parents will have a debriefing for post-vaccination days 1-28 by personal interview. While the window for post-vaccination visits is 28-35 days, the safety observations shall conclude on day 28.

Adverse events meeting the provincial criteria for reporting will be reported to the province in which they occur and to PHAC (VSS), using the prescribed federal-provincial reporting form.

8. SUBJECT COMPLETION AND WITHDRAWAL

Study staff will attempt to contact parents/guardians of subjects who do not return for a scheduled visit, making at least 4 attempts by various means of communication. Each attempt should be documented in the source document/study file.

A subject completing the last scheduled visit will be considered to have completed the study.

Withdrawals will not be replaced. Withdrawals will be documented in the study essential documents file, including the date of withdrawal and reason if known. All data on hand before withdrawal may be included in the study analysis.

9. STATISTICAL ANALYSIS

9.1 Choice of outcomes

The **serologic endpoints** will be based on evaluating antibody responses to HAV vaccine. Seroconversion is defined as change from a negative baseline result to a positive test (≥ 20 mIU/mL). A quantitative result will be provided for each positive result.

1. Primary Outcomes: Seroconversion after the first dose of vaccine.
2. Secondary Outcomes: After the second dose of vaccine
 - a) Seroconversion rates
 - b) Titre of seroconvertors

9.2 Data analysis plan

For comparison of proportions between study groups such as hepatitis A seroconversion the Chi-square test or Fisher's exact test will be used. For comparisons of quantitative variables including serologic titres, Student's t-test will be used. A P value of 0.05 will be considered statistically significant. Multivariate

logistic regression will be used if appropriate to adjust for gender, autoimmune disease, immunosuppressive medication, and presence of autoantibodies with respect to seroconversion status and final titre.

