Hepatitis A vaccine is given as 2 doses; in healthy pediatric hosts, 97-100% will have a protective response a month after the first dose, therefore they are protected for an imminent trip without completing the 2-dose series. Similar results are documented for all inactivated hepatitis A vaccines, which can be used interchangeably. The second dose is given in 6-12 months to ensure lasting protection. In adults with drug-induced immunosuppression, there are recent publications reporting significantly reduced responses to hepatitis A vaccine. An open label study in adults with rheumatoid arthritis on tumor necrosis factor-inhibitors and / or methotrexate, only 10% had an adequate immune response one month after the first dose. This rose to 83% a month after the second dose. This confirms the deleterious impact of immunosuppressive medications on response to this vaccine, most dramatically so in those on increasingly suppressive regimens. The increase in protective rates after the second dose suggests that given sufficient exposure to antigens in the vaccine, these individuals could mount a much better response. However it is unrealistic for most people to plan and prepare for their trips so far in advance, therefore it would be ideal to find a way of protecting immunosuppressed persons more rapidly, in other words after the first dose. An increased dose of vaccine has been shown to be successful in eliciting a protective immune response to hepatitis B in immunocompromised hosts, such as those on dialysis. There has been success with use of double-dose hepatitis A and B vaccines in such populations (personal communication – [name]).

Bringing these various considerations together, a pilot study of vaccine responsiveness of adolescents on immunosuppressive medications for autoimmune diseases to 2 different doses of Hepatitis A vaccine

will confirm the suboptimal response to this important travel vaccine in a pediatric immunocompromised population, and explore one means of improving it.

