2. OBJECTIVES

The objectives of this study of adolescents aged 12 – 15 years with autoimmune diseases treated with immunosuppressive medication are:

1. To confirm whether this population has a reduced immune response to pediatric Hepatitis A vaccine compared to published data on immunocompetent adolescents; and
2. To compare the immunogenicity of 2 formulations of Hepatitis A Vaccine (pediatric and adult) after the first and second doses

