9.2.2 Immune responses

The manufacturer's criteria for positive test result for HAV (≥ 20 mIU/mL) will be applied in the analysis for each formulation. Quantitative titres will be provided for every positive test result.

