9.3 Sample size

Assuming seroconversion rates of 35% (midway between 2 adult studies) to standard dose hepatitis A vaccine and 85% to double dose (response after 2 standard doses in adults), a minimum sample size of 36 (18 in each group; alpha 0.05, power 0.80) is required. Assuming that 20% of the population may be immune due to immigration (25% of the Calgary population are immigrants) from an endemic country, and a drop-out rate of 20%, a total of 60 patients will be enrolled.

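### Section 9.2 gives no scale for the t-test on titres and names logistic regression for a continuous final titre; a log10 analysis with a geometric mean ratio should be written in (minor).

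*Combined protocol and SAP*

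**What the plan says.** Section 9.2 (Data analysis plan) assigns chi-square or Fisher's exact test to proportions and then turns to titres: "For comparisons of quantitative variables including serologic titres, Student's t-test will be used". It mentions no transformation, effect measure or confidence interval. The same section allows, where appropriate, a multivariate logistic regression adjusting for gender, autoimmune disease, immunosuppressive medication and "presence of autoantibodies with respect to seroconversion status and final titre".

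Section 9.1 makes seroconversion after dose 1 the primary outcome. The secondary outcomes, after dose 2, are (a) "Seroconversion rates" and (b) "Titre of seroconvertors". Section 9.2.2 adds: "Quantitative titres will be provided for every positive test result". Objective 2 is "To compare the immunogenicity of 2 formulations of Hepatitis A Vaccine (pediatric and adult) after the first and second doses".

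GMT is defined in the list of abbreviations but appears in no objective, outcome or analysis.

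**The concern.** Two analysts could follow section 9.2 faithfully and report different results from the same data. One would compare arithmetic means. The other, guided by the abbreviation list, would compare geometric means. The P values and the effect estimates could differ, and the choice would be made after the data are in.

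Antibody titres are often right-skewed. If they are here, an arithmetic mean in a group of about 15 can be driven by one or two high values, the pooled SD grows, and a real difference between formulations is more likely to be missed.

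The adjusted analysis has a separate fault that needs no distributional assumption. Binary logistic regression needs a two-level outcome, and final titre is continuous. The only cut-off in the plan is 20 mIU/mL. Dichotomising there would reproduce seroconversion status and would leave no variation at all among seroconverters. As written, the adjusted titre analysis has no usable model.

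**Working it through.** **1. The plan's own figure.** The documents give no sample size or power for titres; the only calculation is for seroconversion (section 9.3). With 35% vs 85%, two-sided alpha 0.05 and power 0.80, the mean proportion is 0.60 and

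n = [1.960 × √(2 × 0.60 × 0.40) + 0.842 × √(0.35 × 0.65 + 0.85 × 0.15)]² / 0.50² = 13.8 per arm.

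The continuity correction gives (13.8/4) × [1 + √(1 + 4/(13.8 × 0.50))]² = 17.6, rounded up to 18. This matches "a minimum sample size of 36 (18 in each group". The primary sample size is not in question.

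**2. Inputs for the titre comparison.**
- From the documents: 18 per arm (9.3). Seroconversion after dose 2 is taken as 83% in both arms, from the adult figure in the introduction ("This rose to 83% a month after the second dose"). That leaves about 18 × 0.83 = 14.9, or 15 seroconverters per arm. Alpha is 0.05 (9.2), taken as two-sided because sidedness is not stated.
- Assumed, not in the documents: log-normal titres, equal log10 SD in both arms (range 0.3 to 0.6), responder GMT 500 mIU/mL in the reference arm, and a true GMT ratio of 2 or 3. The value 500 does not drive the result, because multiplying every titre by a constant leaves both t statistics unchanged.

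**3. Power among seroconverters** (20,000 simulated trials per cell, Student's t-test on each scale):

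| log10 SD | 2-fold, raw | 2-fold, log | 3-fold, raw | 3-fold, log |
|---|---|---|---|---|
| 0.3 | 0.65 | 0.75 | 0.95 | 0.99 |
| 0.4 | 0.37 | 0.51 | 0.71 | 0.88 |
| 0.5 | 0.21 | 0.35 | 0.45 | 0.70 |
| 0.6 | 0.12 | 0.26 | 0.27 | 0.54 |

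The gap is 0.10 to 0.14 for a 2-fold ratio and 0.04 to 0.27 for a 3-fold ratio.

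An analytic check on the log column uses exactly 15 per arm, a 2-fold ratio and SD 0.3. The non-centrality is 0.301 / (0.3 × √(2/15)) = 2.75 on 28 degrees of freedom, which gives power 0.76, against 0.75 simulated with a varying number of seroconverters.

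**4. Type I error** (ratio 1, 18 per arm): 2.9% to 4.4% on the raw scale and 4.6% to 5.2% on the log scale. The raw test is somewhat conservative; it does not produce false positives.

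**5. Larger groups.** With 60 × 0.80 / 2 = 24 per arm after drop-out, and all of them having a titre, power for a 2-fold ratio is 0.86/0.56/0.34/0.20 on the raw scale and 0.93/0.72/0.53/0.40 on the log scale. The direction is the same.

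**6. Precision on the log scale.** With 15 per arm, the 95% CI of the GMT ratio is the estimate multiplied and divided by 10^(2.048 × SD × √(2/15)) = 1.68/1.99/2.37/2.81 for SD 0.3/0.4/0.5/0.6. Intervals this wide tell the reader more than a P value alone.

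**The case against.** The strongest reply is that this is an omission and not a wrong method. Student's t-test names a test, not a scale, and it is valid on log titres. The GMT abbreviation points towards a log scale, and if that was the intention the power loss is zero. This stands, with one limit: an abbreviation that is never used is weak evidence, and parts of the document look carried over from another protocol (section 6.2 is headed as pandemic vaccines).

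A second reply is that the power figures are not this trial's. Data simulated as log-normal with equal log-scale SDs are the case for which the log t-test is designed, so its advantage is largely built in. This also stands. The table shows what is at stake under a plausible assumption; it is not evidence about these titres.

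Neither reply rescues logistic regression for final titre, although that analysis is planned only if appropriate.

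A reader might also infer that the plan hides a selection problem by comparing titres only in seroconverters, a group formed after randomisation. The documents do not support that as a fault. Section 9.1 names the subset in the outcome itself and lists it directly after seroconversion rates, which account for the non-responders. Section 9.2.2 provides quantitative titres for positive results. Nothing presents outcome (b) as a comparison of all randomised subjects.

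**Conclusion.** The point holds as a minor one, in two parts. The model mismatch for adjusted final titre is plain from the text and needs no assumption. The missing scale for the t-test is a gap which, if the section is followed literally, leads to the less suitable analysis. Under assumed log-normality it costs 0.10 to 0.14 in power for a 2-fold ratio at 18 per arm, and it costs nothing if a log scale was already meant.

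The reach is limited to secondary outcome (b) and the conditional adjusted analysis, in a pilot. It would be wrong to conclude that the trial is underpowered for its main question or prone to false positives. The primary outcome is binary and tested by chi-square or Fisher's exact test, the sample size reproduces, and the raw-scale test is conservative. Nor does the log scale make the titre comparison well powered: for a 2-fold ratio it reaches only 0.26 to 0.75 at 18 per arm.

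**What to change.** In section 9.2:
- State that titres are compared by Student's t-test on log10 titre, and that GMT per arm and the GMT ratio with its 95% CI are reported.
- For the adjusted analysis of final titre, name linear regression on log10 titre. Keep logistic regression for seroconversion status.

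This is a wording change, best made before titres are seen by group. It needs no extra subjects, samples or assays. The one trade-off is that the effect is then a ratio of geometric means and no longer a difference in arithmetic means in mIU/mL.

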The study is a prospective, single centre, double-blinded randomized controlled trial whose **goal** is to compare the immune response of a population of immunosuppressed pediatric patients with autoimmune diseases on immunosuppressive medications to two different doses of Hepatitis A vaccine. The objectives are (a) to confirm that adolescents, like their adult counterparts, have a reduced immune response to hepatitis A vaccine, and (b) to compare the immunogenicity of two different dosing options of vaccine for this age group after one and two doses. A total of 60 adolescents aged 12 – 15 years with confirmed autoimmune disease for which they are being treated with an immunosuppressive therapy will be recruited from the Rheumatology and Gastroenterology Clinic at Alberta Children's Hospital (ACH). Those found to have no immunity to hepatitis A will be enrolled. Informed, written consent will be obtained from the parent or guardian of subject, with assent obtained from the study subjects. Subjects will be randomly assigned to two doses of either Avaxim Pediatric® or Avaxim ® (adult) vaccine (Sanofi Pasteur Canada), six months apart, with hepatitis A titres done at baseline and one month after each dose. Both formulations are licensed for this age group.

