4.3 Inclusion criteria

Subjects must meet all of the following inclusion criteria and none of the exclusion criteria to participate in this study.

Criteria that apply to all subjects include:

- Written informed consent provided for the subject by a parent or legal guardian.
- Written informed assent from the participants themselves.

- Subjects whose parents the investigator believes can and will comply with the requirements of the protocol (i.e. return for follow-up visits, record safety observations, able to converse with study personnel and contactable by telephone).
- Age 12 years to 15 years and 5 months
- Confirmed autoimmune disease
- Maintained on any immunosuppressive medication with the exception of pulse steroids

4.4 **Exclusion criteria**

The following criteria apply:

- Systemic hypersensitivity to any Hepatitis A vaccine component such as neomycin, 2-phenoxyethanol, formaldehyde, aluminum hydroxide, Medium 199 Hanks, or Polysorbate 80.
- Thrombocytopenia or any bleeding disorder that contraindicates IM injection or blood collection.
- Receipt of blood or any blood-derived products (including IVIG) within the past 3 months.
- Previous laboratory-confirmed infection with Hepatitis A
- Previous vaccination with any Hepatitis A vaccine

The following conditions are **temporary or self-limiting exclusions** so a subject can be vaccinated once the condition has resolved and no other exclusion criteria exist:

- Current febrile illness or oral temperature of $\geq 38.5^{\circ}\text{C}$ (or equivalent by other route) or other moderate to severe illness within 24 hours before study vaccine administration
- Receipt of any Hepatitis B vaccine within 28 days of planned study vaccine doses. When Twinrix® has been studied, the response to Hepatitis B is amplified by the presence of Hepatitis A. It is unknown whether the reverse is also true.
- Routine childhood vaccines (except MMR and Varicella) must be separated from a study vaccination by at least 7 days.

4.5 **Contraindications to subsequent blood draw**

- Receipt of blood or blood-derived products
- New bleeding disorder that begins after Visit 1
- Receipt of non-study Hepatitis A vaccine

4.6 **Contraindications to subsequent immunization**

- Severe reaction to study Hepatitis A vaccine
- New bleeding disorder that contraindicates IM injection or blood collection.

- Receipt of blood or any blood-derived products.
- Receipt of non-study Hepatitis A vaccine

4.7 **Deviations**

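### Logistic regression is the only adjusted analysis named for final titre, a quantitative outcome; linear regression of log titre should replace it

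*Combined protocol and SAP*

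**What the plan says.** Section 9.2 names three kinds of analysis. Proportions are compared by chi-square or Fisher's exact test. Student's t-test serves for "comparisons of quantitative variables including serologic titres". The only adjusted method is multivariate logistic regression, to be "used if appropriate to adjust for gender, autoimmune disease, immunosuppressive medication, and presence of autoantibodies with respect to seroconversion status and final titre".

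Section 9.1 makes seroconversion after dose 1 the primary outcome. After dose 2 it lists seroconversion rates and "Titre of seroconvertors" as secondary. Seroconversion means going from a negative baseline to at least 20 mIU/mL. Section 9.2.2 adds: "Quantitative titres will be provided for every positive test result".

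The plan gives no other titre threshold, no linear or ordinal model, no covariate coding, no estimator, and no rule for deciding when adjustment is appropriate. On medication, entry requires only: "Maintained on any immunosuppressive medication with the exception of pulse steroids".

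**The concern.** The t-test for titres adjusts for nothing, so logistic regression is the only route the plan offers to an adjusted titre comparison, and in its usual binary form it does not fit that outcome. An analyst would have to pick a threshold or change the model, possibly after seeing the data.

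The same sentence raises a smaller question about seroconversion. The trial is small and the covariate list is long for the number of non-converters expected. Entering the whole list in an ordinary fit would push the estimated odds ratio away from 1 and sometimes leave it without a finite value. What is at stake is the adjusted results only.

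**Working it through.** **Titre.** The one documented threshold can be used in two ways:
- All subjects: at or above 20 mIU/mL versus below. With a negative baseline, this is seroconversion again.
- Seroconvertors only: all are at or above 20 mIU/mL by definition, so the outcome does not vary.

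Neither gives an adjusted analysis of titre. A linear model is feasible. Assume 83% seroconversion after dose 2 in both arms (the adult rheumatoid arthritis figure in section 1) and 18 subjects per arm: 36 × 0.83 = 29.9 seroconvertors. An intercept and five slopes leave 29.9 − 6 ≈ 24 residual degrees of freedom. The documents give no titre mean or SD, so precision cannot be computed.

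**Sample size, reproduced first.** Section 9.3 states "a minimum sample size of 36 (18 in each group; alpha 0.05, power 0.80) is required", for 35% versus 85%. The two-sided normal formula gives (1.96√0.48 + 0.8416√0.355)² / 0.5² = 13.83. The continuity correction gives (13.83/4)(1 + √(1 + 4/(13.83 × 0.5)))² = 17.6, hence 18 per arm. Exact Fisher power at 18 is 0.842. Inflation: 36/(1 − 0.20 − 0.20) = 60.

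**Seroconversion after dose 1.** Three sizes per arm are plausible:
- 18, the stated minimum.
- 24 = 60 × 0.8/2: 20% immune and no loss before the first post-dose sample. Section 8 says "All data on hand before withdrawal may be included in the study analysis".
- 30, if all 60 are non-immune. The Investigator Summary says "Those found to have no immunity to hepatitis A will be enrolled".

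Expected non-converters are n × 0.65 + n × 0.15. Vaccine group plus four two-level covariates is five slopes. The true odds ratio is (0.85/0.15)/(0.35/0.65) = 10.5. Simulation: 6,000 trials per size, covariates at 50% and without effect.

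| Per arm | 18 | 24 | 30 |
|---|---|---|---|
| Expected non-converters | 14.4 | 19.2 | 24.0 |
| Per slope (÷5) | 2.9 | 3.8 | 4.8 |
| Separation, ordinary fit | 11% | 3% | 1% |
| No non-converter in the 85% arm (0.85ⁿ) | 5.4% | 2.0% | 0.8% |
| Median odds ratio, ordinary fit, finite fits | 15.9 | 15.2 | 14.1 |
| Median odds ratio, Firth, all trials | 10.0 | 10.1 | 10.1 |
| Upper/lower ratio of 95% interval, Firth, five slopes | 38 | 21 | 15 |
| Same, Firth, vaccine group only | 25 | 17 | 12 |

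The ordinary-fit medians are 15.9/10.5 = 1.51 and 14.1/10.5 = 1.34 times the truth at 18 and 30 per arm. Repeat simulations gave medians of 15.4 to 16.0, 14.7 to 15.3 and 13.9 to 14.3.

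**Sensitivity.**
- Coding is unstated. If disease and medication had four equally common levels each (an assumption; nine slopes), the ordinary-fit medians would be 22.6, 21.9 and 19.2, with about 40%, 13% and 4% of fits failing.
- At a true odds ratio of 2.79 (35% versus 60%, an assumption) and five slopes, the medians were 3.3 to 3.4, 3.1 to 3.2 and 3.1. That is 3.1/2.79 = 1.11 to 3.4/2.79 = 1.22 times the truth.
- With no true effect there was no bias.
- With five slopes, the ordinary 95% Wald interval covered the design value in 98%, 98% and 96% of finite fits. Type I error was 5.4%, 5.7% and 5.4%.

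**The case against.** On titre, the best defence is that logistic regression need not mean binary. A cumulative (ordinal) model handles a quantitative outcome without a cut-point, and section 9.2 does not say binary. That stands as a limit: the cut-point argument applies to binary logistic regression. It does not rescue the text, because no ordinal model is named. If one was meant, the plan should say so.

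On seroconversion, the defence is stronger:
- The plan does not commit to a full model. Its conditional wording leaves room for fewer covariates, another estimator or no adjustment. A reader might infer that an overfitted model is planned; the text supports only that no criterion is given.
- A reader might also infer that the odds ratio will be inflated by a third to a half whatever the result. That holds only near the design effect, and coverage and type I error are not materially harmed.
- Not every adjusted value above 10.5 is bias. Section 1 expects response to fall with stronger immunosuppression. With one balanced binary covariate of odds ratio 3, 5 or 10 (assumed) and marginal rates of 35% and 85%, the correct conditional odds ratio is 12.2, 14.5 or 20.1. The simulated excess is small-sample bias because its covariates have no effect.
- At 24 and 30 per arm most separation comes from an 85% arm without non-converters (2.0 of 3.2 points and 0.8 of 0.9 points). The unadjusted odds ratio would then be infinite too.

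All four stand, so this half is secondary and conditional.

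**Conclusion.** The titre half holds as written and needs no simulation: the only adjusted method named for final titre does not suit it in its usual binary form, and the one available threshold yields either a duplicate or nothing to model. This should be corrected.

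The seroconversion half holds only under stated conditions: all four covariates entered, ordinary maximum likelihood, rates near 35% and 85%, and covariates without effect. The median odds ratio is then about 14 to 16 against 10.5 with two-level covariates, and more with finer coding.

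A reader might infer that titres cannot be compared at all, or that the trial's main conclusion is biased. The documents support neither. The unadjusted t-test for titres is specified, the primary comparison is an unadjusted chi-square or Fisher test, and the sample size reproduces exactly.

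**What to change.** For final titre, replace logistic regression with linear regression of log10 titre among seroconvertors one month after dose 2, on vaccine group and the four listed covariates. Fix the covariate categories before unblinding. Take autoantibody status from the Visit 1 pre-vaccination sample, since section 5.3.3 does not say which sample counts. Label the analysis supportive. State that seroconvertors are a subset formed after vaccination, so this is not a fully randomised comparison.

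For seroconversion, specify Firth penalised logistic regression with few, pre-specified categories. Recruiting clinic (section 4.2) is one two-group coding of disease already in the documents. Replace the open condition with a stated rule for when adjusted results are reported.

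The cost is SAP wording and a little analysis time; no new data are needed. Categories become coarser and intervals stay wide. Firth with Wald intervals is somewhat conservative at 18 per arm: about 2.6% rejection under no effect, and 77 to 80% at the design rates against 85 to 87% for the ordinary fit. The latter counts only trials with a finite fit; taking the 11% without one as non-rejections gives 0.87 × 0.89 = 77%, so the power loss at the design effect is smaller than it looks.
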